### **5.3. Screen Failure**

A screen failure is defined as any subject who fails Screening assessments or is ineligible based on inclusion/exclusion criteria during Screening or on the Day 1 Pre-operative assessment.

### **5.4. Replacement of Subjects**

Any subject who is withdrawn or discontinued from the study after receiving study drug will not be replaced. Subjects who withdraw consent before dosing may be replaced.

### **5.5. Number of Subjects and Centers**

This study will be conducted at a minimum of 3 study sites in the US. A total of 450 subjects will be randomized (150 per arm) to achieve 130 evaluable subjects per treatment group. An evaluable subject is defined as one who receives study drug, completes surgery, and has at least 2 post-operative pain assessments.

A PK subgroup of 90 subjects (approximately 30 subjects per study arm) will be assessed at 1 site only.

## 6. STUDY TREATMENT

All subjects will be randomized to receive either low-dose XG005, high-dose XG005, or placebo.

XG005 [750 mg Q12 hours]

XG005 [1250 mg Q12 hours]

Placebo [matching tablets Q12 hours]

### 6.1. Description

XG005 drug product is formulated as tablets containing 250 mg of XG005.

Placebo tablets of XG005 are identical in appearance to their respective active drug tablets.

Each treatment group will be administered a total of 5 tablets to maintain the blind and administered as 5 identical blue tablets (low or high XG005 or its placebo) every 12 hours.

### 6.2. Dosing and Administration

Study drug (XG005 low or high dose, or placebo) will be administered as an oral dose 60 minutes prior to surgery on Day 1 then every 12 hours for 72 hours after the time of first dose. The number and strength of active drug tablets to be administered at each dose level is shown in Table 1. Subjects randomized to placebo will receive the corresponding number of placebo tablets.

**Table 1 Dose and Pill Relationship**

Study Arms	1	2	3
Dose Strength	Placebo	XG005 (low dose)	XG005 (high dose)
Dose Levels	No Drug	750 mg	1250 mg
Number of Tablets	5 × XG005 placebo tablets	3 × 250 mg XG005 tablets + 2 × XG005 placebo tablets	5 × 250 mg XG005 tablets

### 6.3. Preparation/Handling/Storage/Accountability

#### 6.3.1. Acquisition and Accountability

The Sponsor will provide adequate quantities of the study drug kits which will include XG005 and matching placebo to each study site.

#### 6.3.2. Product Storage and Stability

All study drugs must be stored at controlled room temperature (20° to 25°C or 68° to 77°F; excursions are permitted between 15° and 30°C [59° and 86°F]) in a secure cabinet or room with

access restricted to necessary clinic personnel. The site will be required to keep a temperature log to establish a record of compliance with storage conditions.

### **6.3.3. Packaging and Labeling**

Sufficient quantities of XG005 tablets and matching placebo tablets will be supplied by the Sponsor or its designee in high density polyethylene (HDPE) sealed bottles with polypropylene child resistant (PPCR) cap with an induction seal liner. In order to maintain the blinding, study drug kits will be provided with appropriate labeling to meet regulatory requirements.

### **6.3.4. Randomization**

The randomization schedule for each treatment group will be generated by Lotus Clinical Research, LLC (Lotus). Subjects who meet all entry criteria will be randomized before pre-surgery dosing on Day 1 by the IXR system.

Study drug kits will be dispensed by the clinical site pharmacist at each study site according to the randomization schedule.

## **6.4. Blinding**

### **6.4.1. Blinding Procedures**

This is a double-blind study. Neither the subjects nor the investigator will be aware of the treatment assignment. Blinding will be maintained throughout the study by using active and placebo dosage forms of identical appearance. Access to the randomization code will be strictly controlled according to the standard operating procedures of the CRO.

### **6.4.2. Breaking the Blind**

A subject or subjects may be unblinded in the event of a SAE, or other event, or if there is a medical emergency where the identity of the drug must be known to properly treat a subject. If a subject becomes seriously ill or pregnant during the study, the blind will be broken only if knowledge of the administered study drug will affect that subject's treatment options. In the event of a medical emergency requiring identification of the study drug administered to an individual subject, the investigator will make every attempt to contact the independent medical monitor to explain the need for opening the code within 24 hours of opening the code. The investigator will be responsible for documenting the time, date, reason for the code break, and the names of the personnel involved.

### **6.4.3. Study Treatment Compliance**

All doses of study drug will be administered in the clinical unit under direct observation of clinic personnel and will be recorded in the eCRF. Clinic personnel will confirm that the subject has received the entire dose of study drug.

The date and time of study drug dosing will be recorded on the appropriate page of the eCRF. If a subject is not administered study drug, the reason for the missed dose will be recorded.

## **6.5. Prior and Concomitant Medications**

Restrictions for prior and concomitant medications and therapies are described in [Section 5.1](#).

### **6.5.1. Prior Medication**

All prior medications received by the subject within 30 days before signing the ICF should be recorded in the subject's eCRF.

### **6.5.2. Rescue Medication**

During the domiciling period, subjects may be administered IV acetaminophen 1 g, Q 6 hours, PRN, up to 4 g in 24 hours. If a patient is unable to tolerate acetaminophen or if there is insufficient pain relief, 50 mg tramadol will be administered Q 4 hours, PRN, up to 300 mg in 24 hours. Intravenous acetaminophen should always be the first rescue medication administered with tramadol being used as the second option.

Prior to receiving any rescue medication, an NPRS assessment must be performed immediately before administering any rescue medication.

### **6.5.3. Concomitant Medication**

Any other concomitant medication deemed necessary for the welfare of the subject (except prohibited medications) during the study may be given at the discretion of the investigator. If a concomitant medication is taken, except for those specified in the protocol, a joint decision will be made by the investigator and the sponsor to continue or discontinue the subject based on the time the medication was administered, its pharmacology and PK, and whether the use of the medication will compromise the safety of the subject or the interpretation of the data. The investigator is responsible for ensuring that details regarding the medication are adequately recorded in the eCRF.

### **6.5.4. Permitted Medications**

Only the protocol-defined rescue medication is permitted in the study. All other analgesics administered will result in a subject terminating early from the study.

No pretreatment for potential nausea and vomiting is permitted. Administration of antiemetic medications are limited to subjects with active vomiting, subjects with a score  $\geq 5$  on the NNRS, or by subject request only.

### **6.5.5. Surgery and Anesthesia**

Subjects will undergo primary, unilateral, first metatarsal Austin bunionectomy. The surgical procedure should be limited to a maximum duration of 90 minutes. End of surgery will be defined as completion of the last suture.

The surgery will be performed under regional anesthesia via a local Mayo block using lidocaine (20 mL, 2.0%) without epinephrine, with IV propofol for sedation.

Propofol induction (dose per discretion of anesthesiologist) will be given as an initial bolus followed by a continuous infusion of up to 250  $\mu$ g/kg/min for intraoperative sedation.

A small dose of lidocaine (up to 5 mL of 1% lidocaine without epinephrine) may be administered to reduce vein irritation at the infusion site.

Intraoperatively, all subjects will be given 50  $\mu$ g of fentanyl IV around the time of induction with propofol.

Once sedated, a Mayo block of the first metatarsal will be induced using lidocaine (20 mL, 2.0%) without epinephrine.

Midazolam 1 mg IV may be administered preoperatively for anxiolysis.

A pneumatic ankle tourniquet inflated between 150 and 250 mmHg will be applied to achieve homeostasis.

## 7. STUDY INTERVENTION DISCONTINUATION AND PARTICIPANT DISCONTINUATION/WITHDRAWAL

### 7.1. Study Stopping Criteria

The following criteria will determine whether to stop study drug dosing. The Investigator and the Sponsor may decide to stop drug administration based on other safety signals not described in the following criteria:

- One drug-related SAE without a clear alternative etiology, or
- Two or more subjects develop a severe adverse event (Grade 3 or above, based on FDA Guidance Toxicity Grading Scale for Healthy Adult and Adolescent Volunteers Enrolled in Preventive Vaccine Clinical Trials, see [Appendix L](#)) possibly related or related to the study drug of the same preferred term or same symptom, or
- Greater than 25% of subjects develop any severe adverse event (Grade 3 or above, based on FDA Guidance Toxicity Grading Scale for Healthy Adult and Adolescent Volunteers Enrolled in Preventive Vaccine Clinical Trials, see [Appendix L](#)) possibly related or related to the study drug.

If one of the above stopping criteria is met, dosing will be stopped and unblinded assessment will be conducted for further decision making.

So far, there have been no identified adverse events of special interests (AESIs) for XG005 in the three completed phase 1 trials, which showed good tolerability and an acceptable safety profile.

### 7.2. Discontinuation of Study Treatment

Subjects can withdraw consent and discontinue from the study at any time, for any reason, without prejudice to further treatment.

The investigator may withdraw a subject from the study if the subject meets any of the following criteria:

- Is noncompliant with the protocol
- Experiences an SAE or intolerable AE(s) that, in the investigator's opinion, requires withdrawal from the study
- Has laboratory safety assessments that reveal clinically significant hematologic or biochemical changes from baseline values
- Develops symptoms or conditions that are listed in the exclusion criteria during study
- Requires a medication prohibited by the protocol (including receiving rescue medication beyond what is allowed per protocol)

- Requests early discontinuation for any reason.

The investigator can also withdraw a subject upon the request of the sponsor, or if the sponsor terminates the study. If withdrawal is considered because of an SAE or intolerable AE, the investigator will confer with the sponsor. If a subject is discontinued because of an AE, the event will be followed until it is resolved, stable, or judged by the investigator to be not clinically significant.

### **7.3. Participant Discontinuation/Withdrawal**

When a subject withdraws from the study, the reason(s) for withdrawal shall be recorded by the investigator on the relevant page of the eCRF. Any subject who fails to return for final assessments will be contacted by the site in a reasonable attempt to have them comply with the protocol. The status of subjects who fail to complete final assessments will be documented in the eCRF.

### **7.4. Early Termination**

Whenever possible, any subject who prematurely withdraws from the study will undergo all EOS assessments per the Schedule of Assessments ([Section 1.2](#)) and the Early Termination assessments that include NPRS, PGA, SIS, RSS and NNRS. Subjects who terminate early from the study will be requested to remain in the clinic for the full 72 hours for continued collection of safety assessments only (vital signs, ECGs, laboratory testing, AE monitoring, and concomitant medications).

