Permitted Medications	
If a subject receives inadequate analgesia from study treatment and allowed rescue medication, they may terminate from the efficacy portion of the study and receive open-label standard of care analgesia excluding NSAIDs or gabapentinoids as per the discretion of the investigator. At the time of receiving standard of care analgesia, the following assessments will be performed prior to receiving standard of care analgesia:
 
 
• NPRS
 
• PGA
 
• PK sample
 
 
Because subjects will remain in the unit and continue to have all other assessments performed there is no need to do anything else at this time. If a subject is not willing to remain in the unit, then they should have all assessments as detailed in the current protocol language for early termination.
 
Subjects who terminate early due to lack of efficacy will continue to receive their allotted study treatment and will continue to undergo all safety and pharmacokinetic assessments as scheduled. These subjects will also continue with all scheduled follow up visits (unless the subject withdraws consent). Subjects who withdraw because of an AE, would not continue to receive study medication.
 
Antiemetics
 
No pretreatment for potential nausea and vomiting is permitted. Administration of antiemetic medications are limited to subjects with active vomiting, subjects with a score <math>\geq 5</math> on the NNRS, or by subject request only.

Study Objectives:	Primary Efficacy

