Safety and PK Endpoints	
Safety
 
Safety and tolerability of XG005 compared with placebo measured by AE reporting (incidence of AEs and SAEs), vital signs, <math>\text{SPO}_2</math>, ECGs, and laboratory values.
 
Sedation will be assessed by study staff by use of the Ramsay Sedation Scale (RSS) when NPRS can be assessed. Nausea will be self-assessed using an 11-point NNRS.
 
Pharmacokinetics
 
Plasma PK parameter endpoints to include the following:
 
 
• Area under the plasma concentration-time curve from time zero to time <math>t</math> of the last measured concentration above the limit of quantification (<math>\text{AUC}_{\text{last}}</math>)
 
• Area under the plasma concentration-time curve from zero to infinity (<math>\text{AUC}_{\text{inf}}</math>)
 
• Maximum plasma concentration (<math>C_{\text{max}}</math>)
 
• Trough plasma concentration prior to each dose (<math>C_{\text{trough}}</math>)
 
• Time to reach maximum plasma concentration (<math>T_{\text{max}}</math>)
 
• Terminal elimination rate constant (<math>\lambda_z</math>) with the respective half-life (<math>t_{1/2}</math>).
 

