## 4. STUDY DESIGN

### 4.1. Overall Design

This is a multi-center, randomized, double-blind, parallel-group, placebo-controlled study in subjects undergoing bunionectomy.

Subjects scheduled for bunionectomy surgery who meet all of the inclusion criteria and none of the exclusion criteria below will be enrolled and randomized.

Eligible subjects will be randomized in a 1:1:1 ratio to receive either 750 mg XG005 (low dose), 1250 mg XG005 (high dose), or placebo. Randomized subjects will receive drug per their treatment allocation as follows:

- 60 minutes prior to surgery, then
- Every 12 hours ( $\pm$  10 minutes) after the first dose for 72 hours.

Subjects and all study staff performing study assessments will be blinded to treatment allocation. To maintain the blind, a total of 5 tablets will be administered to each treatment group: 5 identical blue tablets (low or high dose XG005 or its placebo) at each time point.

Subjects will undergo a Screening Visit (Day -28 to Day -1), Pre-Operative Assessment (within 24 hours prior to surgery), and a Surgery/Treatment Visit (beginning on Day 1), when the following will occur:

- Study medication administered
- Surgery performed within 60 minutes of first study drug administration
- Time of end of surgery recorded (as time of last suture closed)
- Subjects domiciled in research center for at least 72 hours post-surgery
- Efficacy, safety, and PK assessments performed over 72-hour period post-surgery

“Time 0” will be defined as the start time of first dose from which subsequent 12-hour dosing times will be determined. All study efficacy, safety, and PK assessments are anchored to time of end of surgery (last suture). PK sampling timepoints correlate with the collection of the 11-pt NPRS efficacy assessments when they overlap.

Screening will include subjects’ potential placebo response by use of a pre-study personality questionnaire ([Appendix B](#)).

Subjects will be advised at Screening that if they terminate the study prior to 72 hours, it is requested that they remain in the clinic for continued collection of scheduled safety data only.

Subjects will be confined in the clinic from check-in through 72 hours post last dose to monitor subject safety. Subjects will be discharged at a reasonable hour of the day after the end of the 72-hour treatment period, which may include the morning after the end of the 72-hour treatment period.

There will be a Follow-up Visit on Day 15.

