### 8.2. Safety Assessments

The timing and frequency of all safety assessments are provided in the SOA ([Section 1.2](#)). Safety endpoints include monitoring and recording of AEs and SAEs, clinical laboratory results (serum chemistry, hematology, coagulation, and urinalysis), 12-lead ECG results, and vital signs measurements (blood pressure [systolic and diastolic], heart rate, respiratory rate, oral body temperature, and continuous pulse oximetry), and recording of relevant safety data.

Trained staff on hand in the research unit will monitor respiratory safety via respiration rate, continuous pulse oximetry and oxygen saturation ( $\text{SpO}_2$ ) checks every 12 hours post-end of surgery within a  $\pm 10$ -minute window, and somnolence if observed by Staff at times other than

when a formal assessment of somnolence is scheduled. The Ramsay Sedation Scale (RSS, [Appendix G](#)) will be used as an assessment of sedation (somnolence) with the same time sequence as the NPRS determination, but with a window of  $\pm 15$  minutes. A Columbia-Suicide Severity Rating Scale since last visit ([Appendix K](#)) will be administered at 72 hours post treatment and at the follow-up visit and at the end of study visit/early termination visit.

For all safety assessments, the investigator will determine whether results are clinically significant, which is defined as any variation in a result that has medical relevance and that may result in an alteration in medical care (e.g., active observation, diagnostic measures, or therapeutic measures). If clinical significance is noted, the result and reason for significance will be documented and an AE reported on the AE page of the subject's electronic case report form (eCRF). The investigator will monitor the subject until the result has reached the reference range or the result at Screening, or until the investigator determines that follow-up is no longer medically necessary.

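### Sections 6.5.4 and 7.4 do not carry the synopsis rule for lack-of-efficacy subjects, so scheduled sedation scores could stop while dosing continues

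*Combined protocol and SAP*

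**What the plan says.** Three parts of the protocol govern a subject who needs analgesia beyond the allowed rescue.

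- **Section 6.5.4, Permitted Medications:** "All other analgesics administered will result in a subject terminating early from the study". It says nothing about continued dosing.
- **Section 7.4, Early Termination:** RSS and the nausea scale (NNRS) are among the ratings taken at termination. Early terminators are then asked to stay for the full 72 hours for "continued collection of safety assessments only (vital signs, ECGs, laboratory testing, AE monitoring, and concomitant medications". Neither RSS nor NNRS is among these five items.
- **Section 1.1, Synopsis, Permitted Medications row:** a subject with inadequate analgesia may leave the efficacy part of the study and receive open-label standard of care, excluding NSAIDs and gabapentinoids. NPRS, PGA and a PK sample are taken first. Nothing more is needed then: "Because subjects will remain in the unit and continue to have all other assessments performed". The row goes on: "Subjects who terminate early due to lack of efficacy will continue to receive their allotted study treatment and will continue to undergo all safety" and PK assessments as scheduled. Only those who leave are sent to the early-termination procedures: "If a subject is not willing to remain in the unit, then they should have all assessments as detailed in the current protocol language".

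RSS is a safety measure in the protocol's own terms. The synopsis safety endpoints state "Sedation will be assessed by study staff by use of the Ramsay Sedation Scale (RSS) when NPRS can be assessed", and Section 8.2 says that RSS "will be used as an assessment of sedation (somnolence) with the same time sequence as the NPRS determination". It is also a tertiary endpoint in Section 3.

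**The concern.** Sections 6.5.4 and 7.4 share a trigger, early termination from the study, and together they bring every subject given another analgesic under the five-item list. The synopsis sends the same lack-of-efficacy subjects down a different path if they stay in the unit: still dosed and still fully assessed. Sections 6.5.4, 7.2 and 7.4 do not repeat that rule, or its split between subjects who stay and those who leave. The protocol does not say which text prevails.

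At stake are scheduled, graded sedation scores in a group where they are informative. These subjects would still be taking a prodrug of pregabalin and naproxen every 12 hours while receiving open-label analgesia that may include an opioid. Section 2.3 reports somnolence as the most common adverse event in the Phase 1 multiple-dose cohort of the tablet formulation (7 of 24 XG005 subjects, 29%).

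**Working it through.** **Step 1. Compare the instructions for a lack-of-efficacy subject who stays in the unit.**

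| Item | Synopsis | Sections 6.5.4 and 7.4 |
|---|---|---|
| Study drug | Continues | Not addressed |
| Scheduled RSS | Continues (a safety assessment) | Not on the list |
| Scheduled NNRS | Continues (among the other assessments) | Not on the list |
| SpO2 | Continues (a safety assessment) | Not named |
| PK samples | Continue | Not on the list |
| Vital signs, ECGs, laboratory tests, AEs, concomitant medications | Continue | Continue |

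**Step 2. See what each way of following the protocol produces.**

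- Synopsis in full: nothing is lost.
- Sections 6.5.4 and 7.4 only: scheduled RSS stops, but nothing there tells the site to keep dosing.
- Dosing from the synopsis, collection list from Section 7.4: scheduled RSS stops in a dosed subject.

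Only the third is the case of concern.

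**Step 3. Count what would be at risk in that third case.** The inputs are:

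- RSS hours after end of surgery (Schedule of Assessments), 20 in all: 0, 1, 2, 3, 4, 6, 8, 10, 12, 16, 20, 24, 30, 36, 42, 48, 54, 60, 66, 72.
- NNRS hours (Section 8.1), 7 in all: 1, 4, 8, 12, 24, 48, 72.
- Doses (Section 6.2), in hours after the first dose: 0, 12, 24, 36, 48, 60 and possibly 72. Whether a 72-hour dose is given is not clear, hence a range of one dose.
- Offset between the clocks: first dose 50 to 70 minutes before surgery, plus surgery of up to 90 minutes (lower end assumed to be 15 minutes). This is (50 + 15)/60 = 1.1 h to (70 + 90)/60 = 2.7 h.

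Scores at risk are those scheduled strictly after the stop. Doses still due are those later than the stop hour plus the offset. The stop hours are assumptions.

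| Assumed stop (h after surgery) | Hours after first dose | RSS at risk | NNRS at risk | Doses still due |
|---|---|---|---|---|
| 4 | 5.1–6.7 | 15 of 20 | 5 of 7 | 5–6 |
| 8 | 9.1–10.7 | 13 of 20 | 4 of 7 | 5–6 |
| 12 | 13.1–14.7 | 11 of 20 | 3 of 7 | 4–5 |
| 24 | 25.1–26.7 | 8 of 20 | 2 of 7 | 3–4 |

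For Hour 12, the remaining RSS hours are 16, 20, 24, 30, 36, 42, 48, 54, 60, 66 and 72, which is 11. The remaining doses are at 24, 36, 48 and 60 hours, which is 4, or 5 with a 72-hour dose.

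The documents give no rate of lack-of-efficacy stops, so these counts are per subject and cannot be scaled to the trial.

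**The case against.** The strongest reply is that the synopsis addresses exactly this subject and puts continued dosing and continued safety assessment in one sentence. A site must obey half of that sentence and ignore the rest before a dosed subject goes unrated. Section 7.4 is the general rule, and also covers subjects withdrawn for adverse events, who are no longer dosed. This stands, and it is why the point is minor. It does not remove the conflict, because Section 6.5.4 uses the very words that trigger Section 7.4.

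It can also be said that the five items only illustrate safety as opposed to efficacy. Section 4.1 supports this: "it is requested that they remain in the clinic for continued collection of scheduled safety data only", with no list. The Section 7.4 wording nevertheless follows a limiting word and carries no sign of being an example, so a site could fairly read it as closed.

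Other monitoring also stands. AE monitoring, continuous oximetry during confinement (Schedule of Assessments, footnote n) and staff-observed somnolence (Section 8.2) would still pick up clinical events. They do not replace scheduled scores comparable across arms.

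Three stronger readings are tempting, and the documents do not support them.

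- **That the protocol directs sites to dose without sedation ratings, or that scores will be lost.** No single section says this; it takes the mixed reading in Step 2.
- **That RSS lapses once NPRS stops,** because footnote u ties it to the NPRS rating. The RSS row of the Schedule lists all 20 hours, and Section 8.2 refers to the time sequence.
- **That nausea is affected on the same footing, so worst observation carried forward should give way to observed scores.** Sections 3 and 8.1 treat NNRS mainly as efficacy, although the synopsis also lists it under safety. Cumulative nausea through 24 hours comes eighth and ninth of ten ranked secondary tests. How to treat scores after open-label analgesia is an estimand choice on which statisticians may differ, not a wording error.

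**Conclusion.** The concern holds as a minor inconsistency between current sections. Section 7.4, reached through Section 6.5.4, gives a narrower collection list than the synopsis gives for subjects whom the synopsis keeps on study drug. RSS is the clear omission, since the protocol itself classes it as safety.

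The size is conditional: 8 to 15 of 20 scheduled RSS scores per affected subject for assumed stops between Hour 24 and Hour 4, and 11 of 20 at Hour 12. It requires a site to dose under the synopsis and collect under Section 7.4. Early stops such as Hour 4 are the upper end, since study drug and the allowed rescue must first prove inadequate. The RSS rating at termination is still taken. The primary endpoint (SPI48) uses neither RSS nor NNRS and is unaffected. RSS is not in the formal testing sequence.

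**What to change.** Carry the synopsis rule into Sections 6.5.4 and 7.4, including the split between subjects who stay in the unit and those who leave. In Section 7.4, state for lack-of-efficacy subjects who stay that:

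- study drug continues;
- all scheduled safety assessments continue through 72 hours, naming RSS at its listed hours and SpO2;
- PK sampling continues for those in the PK subgroup;
- NNRS continues at its scheduled hours, as one of the other assessments that the synopsis keeps.

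The five-item list can remain for early terminators no longer on study drug.

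The cost is protocol wording and a few minutes of staff time per rating in subjects who are already in the unit and monitored. No change to the analysis or the missing-data rules is needed.
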